#### Additional analyses:

- FOR ALL OUTCOMES: We will repeat the models indicated above, adding an interaction term for RandomGrp \* ADRDstatus
- FOR ALL OUTCOMES: Repeat the models above (excluding model with interaction between randomization assignment and ADRD) separately for those with ADRD and those without ADRD.
- Costs of care:
  - Time frames:
    - 1 month following randomization
    - 3 months following randomization
  - Separate analyses for the following outcomes include:
    - Total costs
    - Variable direct costs
    - Fixed direct costs
    - Indirect costs
    - Post-discharge costs

- We will use generalized linear modeling for these analyses. For each analysis we will do preliminary investigation of the family and link that best fit the data (with fit based on AIC and BIC), perhaps restricting these preliminary analyses to investigation of the gamma and inverse Gaussian families, and to log and square root links.
- RE-AIM analysis of intervention group  
For all patients in the intervention group:
  - Tests of the association of Jumpstart format (PDF vs. HTML) with each of the study outcomesFor all patients whose clinicians received the HTML-formatted Jumpstart form:
  - Tests of the association of clinician use of the form (0=no clinicians opened the Jumpstart form, 1=one or more clinicians opened it) with each of the study outcomes
  - Outcome: 0=no clinicians opened the Jumpstart form, 1=one or more clinicians opened it  
Predictors: hospital site, serviceFor all clinicians who received HTML-formatted Jumpstart forms:
  - Outcome: 0=clinician did not open the form; 1=clinician opened the form.
  - Predictors: hospital site, service, clinician's training year (not sure what to do if the clinician was in different training years for different patients).Method: binary logistic regression – either a complex model clustered on clinician (which would ignore cross-clustering on patient) or a multi-level model cross-clustered on clinician and patient.

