For the analysis of the other outcomes, we will use a strategy similar to that for the primary outcome. For continuous outcomes (e.g., ICU-free days, HADS score), the effect of intervention will be quantified by a difference in means. For survey outcomes which are collected at more than one time point after randomization, we will use a mixed model to account for the correlation between repeated measures. Our initial model will allow the average response to be different at each time point, but assume the intervention has the same effect at each time. We will also allow the effect of intervention to be different across time by including an interaction between time and intervention. The advantage of using the data at the multiple time points and a mixed model approach is that we can gain precision; it also allows for missing responses, assuming responses are missing at random. Missing data are more of an issue for the survey outcomes than the primary outcome; we will quantify the amount and type of missing data, evaluate associations of missingness with participant characteristics, and apply appropriate methods to account for missing data.⁶¹

c) Evaluate implementation and identify barriers and facilitators to future implementation.

We will perform thematic content analysis of transcribed interviews to explore feedback on the intervention, ways to improve intervention implementation, and aspects of care not adequately addressed by the intervention.⁶²⁻⁶⁴ Interview guides and analyses will be guided by the RE-AIM and CFIR frameworks as described above.³⁸⁻⁴² Qualitative data will be imported to analytic software (Dedoose), where investigators will perform the following analytic steps using an iterative approach to thematic analysis⁶⁵: 1) initially code

material, devising a coding framework and using that framework to reduce the text into smaller segments; 2) identify themes from the coded text; 3) construct thematic networks that include basic themes, organizing themes and global themes; 4) describe and summarize thematic networks; and 5) interpret patterns that have emerged in and across thematic networks.

7) Sample size

a) Sample size considerations for the primary outcome

The focus for sample size considerations is the primary outcome: proportion of patients with documented goals-of-care discussions within 30 days after randomization.

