Cost assessments for Aim 1 are limited to costs available in the UW Medicine EHR, and we will not be able to assess costs from other healthcare systems after hospital discharge. Most of the benefits we anticipate for this intervention will occur during the hospitalization, although there may be ongoing reductions in costs after hospitalization related to changes in the goals of care as a result of the intervention. We will evaluate for such effects in Trial 2, and the limitation of not having access to these costs from outside UW Medicine in Trial 1 is diminished somewhat because this is a randomized trial.

11) Anticipated findings

These interventions use the EHR to identify patients who should have documentation of a goals-of-care discussion but do not, and then prompt and guide such discussions with either: a) a clinician-facing prompt and guide for clinicians only, along with information about prior advance care planning completed prior to the hospitalization; or b) a bi-directional, patient-specific intervention that provides patient-specific support to clinicians, patients and family members. We anticipate that both interventions will be effective compared to the usual care arm, and that this study will provide important options for healthcare systems. Economic analyses will allow us to evaluate the effect on costs of care, after factoring in the costs of implementing these interventions, to enhance dissemination. If either or both of these interventions are not effective, the results

and the interviews in Aim 3 will provide important information to shape, direct and deliver future interventions.

References

4. Halpern SD. Toward Evidence-Based End-of-Life Care. *N Engl J Med* 2015;373:2001-3.
5. Halpern SD. Goal-Concordant Care - Searching for the Holy Grail. *N Engl J Med* 2019;381:1603-6.

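### Post-discharge cost will contain zeros, at which the planned AIC/BIC choice between gamma and inverse Gaussian models is unusable or arbitrary, and no common effect measure is set for the five cost outcomes

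*SAP*

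**What the plan says.** **SAP, Additional analyses (Costs of care).** Five outcomes are listed: total, variable direct, fixed direct and indirect costs, and "Post-discharge costs". Each is analysed over "1 month following randomization" and over three months. The method is stated as "We will use generalized linear modeling for these analyses". For each analysis there is to be a "preliminary investigation of the family and link that best fit the data (with fit based on AIC and BIC"), with the search narrowed tentatively: "perhaps restricting these preliminary analyses to investigation of the gamma and inverse Gaussian families, and to log and square root links". The SAP does not mention zero costs, a two-part model, how the gamma dispersion is handled, or which contrast will be reported. Its general rule is that regression models adjust for hospital site and ADRD status only.

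**Protocol, section 6 b).** Other outcomes follow a strategy similar to that for the primary outcome, which is linear regression with robust standard errors. The section adds: "For continuous outcomes (e.g., ICU-free days, HADS score), the effect of intervention will be quantified by a difference in means". Costs are among the outcomes in section 5 a) and Table 1.

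**Protocol, section 10 g).** Aim 1 costs come only from UW Medicine's own records. The section accepts the consequence: "we will not be able to assess costs from other healthcare systems after hospital discharge".

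**The concern.** Zeros are built into post-discharge cost. A patient who dies in the index stay has none, nor does one still in hospital when the window closes. A survivor whose later care is all elsewhere has none on record. AIC and BIC need a finite likelihood, and both families named are distributions for strictly positive values.

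The analyst would therefore have to improvise after seeing the data. One obvious way out, analysing positive costs only, would compare groups defined by what happened after randomization. It would miss any effect that works through fewer patients having a cost at all.

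There is also a reporting gap. If family and link are chosen separately up to ten times (five outcomes, two windows), one effect may appear as a ratio and the next on a square-root scale. Section 11 of the protocol intends to set cost effects against the cost of running the intervention. That needs a difference in money.

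**Working it through.** The documents give no mean cost, variance, share of zeros or target effect, so there is no planned figure to reproduce. Zero shares, cost levels and effects below are assumptions. Only the size of 1000 per arm comes from the protocol (section 7 a).

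**1. Likelihood at zero.**
- Gamma, mean μ and shape k: log f(y) = k log k − k log μ + (k − 1) log y − k y/μ − log Γ(k). As y → 0 the term (k − 1) log y goes to +∞ if k < 1 and to −∞ if k > 1. Only at k = 1 (dispersion fixed at 1) is the value finite, namely −log μ.
- Inverse Gaussian, with parameter λ: log f(y) contains −1.5 log y and −λ(y − μ)²/(2μ²y). It has no finite value at y = 0.

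With dispersion fixed at 1, the two links could still be compared within the gamma family, but gamma could not be compared with inverse Gaussian.

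**2. Fitted check.** One simulated data set per zero share; n = 2000, gamma costs with shape 0.8, true mean ratio 0.90, log link, dispersion estimated.

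| Share of zeros | Gamma AIC | Inverse Gaussian AIC |
|---|---|---|
| 0% | 16,860 | 96,903 |
| 10%, 30%, 50% | −∞ | undefined |

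**3. Replacing zeros by a small constant c** (30% zeros). Gamma AIC was 5,320 at c = 0.000001 and 14,834 at c = 1, while the gamma coefficient hardly moved (−0.226 and −0.219). Inverse Gaussian AIC ran from about 4.35 billion down to 51,629. Gamma had the lower AIC at every c tried, so the ranking of families did not flip here. The size of the gap, however, is set by an arbitrary constant.

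**4. Keeping zeros in the gamma/log estimating equation.** The equation Σ x(y − μ)/μ = 0 is finite at y = 0.
- In a data set with 30% zeros, standardising over site and ADRD gave a mean difference of −2.78 cost units, against −2.80 from linear regression.
- In 200 simulated trials of 1000 per arm (60% v 54% with any cost), it gave a mean ratio of 0.913 and a difference of −1,087. Linear regression on the same data also gave −1,087. The assumed true values are 0.90 and −1,200; the gap is simulation noise.

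**5. Dropping zeros (not stated in the SAP).** Assume 60% v 54% have any cost, with mean 20,000 among users in both arms.
- All patients: 0.60 × 20,000 = 12,000 and 0.54 × 20,000 = 10,800. The difference is −1,200 and the ratio 10,800/12,000 = 0.90.
- Positives only: 20,000/20,000 = 1.00.
- In a separate set of 200 simulated trials of 1000 per arm (cost CV 1.5), positives-only gamma gave a ratio of 1.006, and linear regression with zeros kept gave −1,174 on a control mean of 11,919. With zero shares of 30% v 37% the figures were 1.007, and −1,361 on 13,851.

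**6. Effect scale.** For a mean ratio of 0.90:

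| Baseline mean | Difference | Log-link coefficient | Square-root-link coefficient |
|---|---|---|---|
| 10 | −1 | −0.105 | −0.162 |
| 20 | −2 | −0.105 | −0.229 |
| 40 | −4 | −0.105 | −0.325 |

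Neither coefficient is a difference in means, and the two are not comparable across outcomes fitted with different links.

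**The case against.** The strongest defence has four parts.

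- **A GLM is a defensible choice for skewed costs.** It models the mean of raw cost, so a mean difference can be derived by standardisation. This stands. A reader might infer that the planned models cannot deliver a difference in means, or that they break down altogether at zero. Step 4 shows otherwise for gamma/log. What fails is the selection step, and the missing piece is a commitment to the contrast.
- **The exposure is narrow.** Patients are already inpatients at enrollment, so total cost should almost never be zero. Aim 1 itself names cost during the hospitalization. This also stands: the zero problem falls mainly on one of five outcomes, listed under additional analyses.
- **Dropping zeros is nowhere in the SAP.** This is true. Step 5 shows what one improvised remedy would do, not what the plan does.
- **The wording is tentative, and section 6 b) does not list costs among its examples.** This stands in part. Other families are not excluded, but AIC/BIC is the stated criterion and both families named are unsuited to zeros. Costs are a continuous outcome under a general rule, even though they are not named in it.

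**Conclusion.** The point holds for post-discharge cost. The stated AIC/BIC choice is unusable there or depends on an arbitrary constant, and the SAP has no rule for zeros. The failure at zero follows from the likelihoods whatever the share of zeros, apart from the gamma case with dispersion fixed at 1. If zeros were dropped, a true mean ratio of 0.90 could be reported as about 1.0. That size rests on the assumed 60% v 54% and equal cost among users. It illustrates bias, not power.

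For all five cost outcomes there is a second, milder gap. The scale may differ from one outcome to the next, and the SAP does not commit to the protocol's difference in means.

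The documents do not support reading this as a fault in the whole cost analysis. The primary outcome is untouched, and index-hospitalization cost is not materially affected by zeros.

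**What to change.** **Post-discharge cost, both windows.** Keep every randomized patient, with zero costs entered as zero. Replace the AIC/BIC search with one model fixed in advance that allows zeros, adjusted for site and ADRD. Either of these would do:
- linear regression with robust standard errors; or
- a two-part model (logistic for any cost, gamma/log for positive cost), combined into a mean difference with a bootstrap confidence interval.

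**All five cost outcomes.** State that the reported effect is the adjusted difference in mean cost with its confidence interval, obtained by standardisation wherever a GLM is kept. Replacing GLMs by linear regression for the other four outcomes is optional.

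**Cost.** A few lines of SAP text and slightly more code. If linear regression is chosen, the interval may be wider than that of a well-fitting GLM when costs are very skewed.
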